Study site personnel must alert a study investigator of any serious and study drug or study procedure related adverse event within 24 hours of investigator awareness of the event. Alerts issued via telephone are to be immediately followed with official notification on the adverse event case report form.

All AEs that do not meet any of the criteria for serious should be regarded as non-serious AEs.

- **Preexisting Condition:** A preexisting condition is one that is present at the start of the study. A preexisting condition will be recorded as an AE if the frequency, intensity, or the character of the condition worsens during the study period.

- **Post-study Adverse Event:** All unresolved AEs will be followed by the Investigator until the events are resolved, the subject is lost to follow-up, or the AE is otherwise explained. At the last scheduled visit, study personnel will instruct each subject to report any subsequent event(s) within 3 months of study completion that the subject, or the subject's personal physician, believes might reasonably be related to participation in this study.

- ***Abnormal Laboratory Values:*** A clinical laboratory abnormality should be documented as an AE if any 1 of the following conditions is met:
  - The abnormality suggests a disease and/or organ toxicity that worsened from the time of enrollment, or
  - The abnormality is of a degree that requires active management; e.g., change of dose, discontinuation of the drug, more frequent follow-up assessments, further diagnostic investigation, etc.
- ***Continuous SAEs of interest monitoring:*** The following SAEs will be continuously reported to the DSMB: deaths. Cardiovascular events (need for vasoactive drugs or fluids for hypotension), and respiratory events (worsening hypoxia, worsening acute respiratory distress syndrome, or new respiratory failure) will be continuously reported to the DSMB within 24 hours of recognition for safety reasons. While they will be reported continuously, they will not necessarily be filed as SAEs unless the investigator deems it to be related to study procedures (see below)

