- ***Other outcomes that may be exempt from adverse event reporting:*** Study specific outcomes as outlined in 5.1 and 5.2 are exempt from adverse event reporting unless the investigator deems the event to be related to the study procedures (or of uncertain relationship) or if the event leads to discontinuation of study procedures. The following are examples of events that will be considered study specific clinical outcomes and will be systematically tracked through the study design. The rationale for this criteria is that these events are likely to be present in a large proportion of the study population, and relatedness will be subject to significant subjective assessment, making adverse event reporting can be sporadic and inconsistent. Therefore, events more likely to be truly related to a study intervention are better treated by consistent tracking through the systemic design and collection of potentially related adverse events:
  - Respiratory events: decreased PaO2/FiO2, hypoxia, worsening acute respiratory distress syndrome, or respiratory failure.
  - Cardiovascular events: (need for vasoactive drugs or fluids for hypotension)
  - Hepatic events: hepatic injury or liver dysfunction that leads to an increase from baseline in the serum level of bilirubin.
  - Renal events: renal failure, renal insufficiency, or renal injury that leads to an increase from baseline in serum creatinine.
  - Hematologic/coagulation events: coagulopathy, disseminated intravascular coagulation, thrombocytopenia, or thrombocytosis.
  - Changes in serum sodium and potassium
- ***Scales Used to Grade Severity of Adverse Events:*** All AEs will be graded in the following manner:
  - Grade 1 (Mild): Events require minimal or no treatment and do not interfere with the participant's daily activities.
  - Grade 2 (Moderate): Events result in a low level of inconvenience or concern. Moderate events may cause some interference with functioning.

- Grade 3 (Severe): Events interrupt a participant's usual daily activity and may require systemic drug therapy or other treatment. Severe events are usually incapacitating.
- Grade 4 (Life-threatening): Any adverse drug experience that places the participant, in the view of the Investigator, at immediate risk of death from the reaction as it occurred (i.e., it does not include a reaction that had it occurred in a more severe form, might have caused death).
- Grade 5 (Death)

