[Patient Safety] A recommendation to suspend, alter the study, or stop for harm would occur if during continuous monitoring there is strong evidence that the rate of IRB-reported SAEs was significantly higher in the experimental group than in the placebo group. SAEs (including increasingly level of ventilator support and initiation of vasopressors, the two SAEs of interest) will be reported within 24 hours, allowing for continuous study monitoring. For the inpatient cohort, we propose formal interim analyses for safety at 10%, 20%, and 30% of enrollment. A 50% preplanned interim analysis for safety, efficacy, and futility is planned with specific stopping rules provided to the DSMB as a guide. Assuming a baseline mortality rate of 10%, this corresponds to formal hypothesis testing after every ~2 events initially, and decreasing as data accumulate. Despite the lower number of formal preplanned analyses, the DSMB will still receive near *real-time reporting of deaths*, and can deviate from this strategy and perform earlier testing if desired.

They retain authority to change this plan if the continuous reporting suggests harm prior to the first formal planned assessment if they feel that a formal hypothesis test is warranted. In addition, the DSMB may request additional safety assessments after the 50% assessment, if they feel that additional formal testing is needed.

[Efficacy] – A preplanned interim analysis at 50% of enrollments will assess for early efficacy or futility.

The DSMB will operate in accordance with guidelines established by the FDA in “Guidance for Clinical Trial Sponsors: Establishment and Operation of Clinical Trial Data Monitoring Committee” jointly published by the CBER, CDER and CDRH of the FDA (<https://www.fda.gov/regulatory-information/search-fda-guidance-documents/establishment-and-operation-clinical-trial-data-monitoring-committees>) . The key elements include:

1. Expertise and independence: The members must have expertise in the area of study, not be study authors and have no financial conflict of interest.
2. Members will sign a confidentiality agreement.
3. It is preferred that the DSMB have a face-to-face initial meeting, but can meet by telephone thereafter more frequently.
4. All meetings must follow standard operating procedures (SOPs).

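### The only stated stop-for-harm criterion counts undefined IRB-reported SAEs, the protocol conflicts on which events enter that count, and renal and potassium events have no stated DSMB report

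*Combined protocol and SAP*

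**What the plan says.** **The criterion.** Section 18.3 (Patient Safety) sets the test for a recommendation to suspend, alter or stop because of harm. The trigger, applied to continuously monitored data, is that "there is strong evidence that the rate of IRB-reported SAEs was significantly higher in the experimental group than in the placebo group". The term IRB-reported SAEs is not defined in the protocol. The same paragraph describes SAEs as "including increasingly level of ventilator support and initiation of vasopressors, the two SAEs of interest", to be reported within 24 hours. For the formal looks it says "we propose formal interim analyses for safety at 10%, 20%, and 30% of enrollment", and adds a 50% analysis "with specific stopping rules provided to the DSMB as a guide".

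**The filing rules in section 18.2.**
- *Definition of a Serious Adverse Event*: SAEs are collected for the first 15 study days whatever the investigator thinks of causation.
- *Continuous SAEs of interest monitoring*: deaths are reported continuously. Cardiovascular and respiratory events "will be continuously reported to the DSMB within 24 hours of recognition for safety reasons", but "they will not necessarily be filed as SAEs unless the investigator deems it to be related to study procedures".
- *Other outcomes that may be exempt*: "Study specific outcomes as outlined in 5.1 and 5.2 are exempt from adverse event reporting". Three things bring an event back: the investigator judges it related, its relationship is uncertain, or it causes study procedures to be discontinued. The listed examples include respiratory events, hypotension needing treatment, renal events, and changes in sodium and potassium. *Recording and Documentation* repeats the carve-out.
- *Abnormal Laboratory Values*: an abnormality is documented as an AE if it suggests organ toxicity that has worsened since enrollment, or if it needs active management. There is no attribution test.

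**The protocol's own view of these data.** Section 13.1 puts symptomatic hypotension, worsening renal function and electrolyte abnormalities among losartan's most severe risks. Section 3.4 prefers systematic tracking of hypotension and kidney injury because AE reporting can introduce bias. The exemption in 18.2 is justified on the ground that AE reporting of such events can be sporadic and inconsistent.

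**The concern.** A stop-for-harm comparison needs a numerator that two people would count the same way. Here one reader of 18.2 and 18.3 could count every vasopressor start or ventilator escalation, while another could count only those an investigator attributed to study procedures. For renal and potassium events the question is sharper. They are on the exempt list, they are absent from the 24-hour DSMB list, and no DSMB report names them. They would enter the criterion only if filed as SAEs.

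The protocol tracks hypotension and kidney injury as outcomes precisely because it distrusts AE reporting for them, yet it does not state the harm criterion on those tracked outcomes. If the exemption governs, a real excess on losartan would be compared on a reduced count, and the DSMB would be less likely to see it as significant.

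**Working it through.** **1. The plan's own figure.** The only number attached to the monitoring rule is about 2 events between the early looks at 10% mortality. Inputs: 200 participants (section 10.2), looks every 10% of enrollment at first, and 10% mortality (section 18.3). Expected deaths = 200 x 0.10 x 0.10 = 2.0; with 220 participants, 2.2. The figure reproduces, and it shows that the text ties the formal looks to deaths, which are not on the exempt list.

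**2. The filing rules side by side.** All are in section 18.2 unless marked.

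| Event | Rules that would count it | Rules that would leave it out | Stated route to the DSMB |
|---|---|---|---|
| Death | SAE definition | none | continuous |
| Vasopressor start, hypotension treated | SAE collection to day 15 if serious; 18.3 calls vasopressor start an SAE of interest | continuous-monitoring rule (filed only if related); exempt list | within 24 hours |
| Respiratory worsening | SAE collection if serious; 18.3 calls ventilator escalation an SAE of interest | the same two rules | within 24 hours |
| Renal failure or injury | SAE collection if serious; laboratory rule (as an AE) | exempt list | none named |
| Potassium change | SAE collection if serious; laboratory rule (as an AE) | exempt list | none named |

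Two details matter. First, the exempt list has three exceptions (related, of uncertain relationship, or leading to discontinuation), but the continuous-monitoring rule has only one (related). A hypotension event of uncertain relationship is therefore filed under one paragraph and not necessarily under the other. Second, the exemption refers to outcomes in 5.1 and 5.2, which are Screening and Enrollment. The outcomes are in section 3.

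**3. Illustration of the effect if the filter applies.** Event rates, filing fractions and test are all assumed; none is in the documents. Inputs: 50 per arm (half of 200, allocated 1:1), event rates p0 on placebo and p1 on losartan, and the same fraction f of events filed in both arms. Filed rates are f x p0 and f x p1. The chance of a significant excess is the sum, over all pairs of counts with losartan higher and two-sided Fisher p at or below 0.05, of Bin(x; 50, f x p0) x Bin(y; 50, f x p1).

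| Filed fraction f | 10% v 25% | 20% v 40% |
|---|---|---|
| 1.00 | 0.410 | 0.515 |
| 0.90 | 0.352 | 0.452 |
| 0.50 | 0.137 | 0.195 |

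For example, at f = 0.5 the first pair becomes 5% v 12.5%, and the chance falls by (0.410 - 0.137) / 0.410 = 67%. At f = 0.9 it falls by (0.410 - 0.352) / 0.410 = 14%. Because f is the same in both arms, this is lost power and not bias.

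**The case against.** The strongest reply is that the SAE rule collects SAEs to day 15 regardless of causation, and the criterion counts SAEs, so there may be no filter at all. The laboratory rule points the same way for creatinine and potassium. This stands to the extent that the filter cannot be called a settled fact. It does not remove the problem, because the exemption paragraphs say otherwise and nothing states which rule prevails.

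A second reply is that the DSMB is well informed. Deaths, hypotension and respiratory events reach it continuously or within 24 hours. Section 13.1 promises it data on hypotension and shock, and sections 6.1 and 16.10 give it general access to study data. Section 18.3 says a recommendation would occur if the criterion is met, not only if, and lets the board test earlier or change the plan. All of this stands. A reader might infer that the DSMB cannot see or act on these harms; the documents do not support that. What remains is that receiving an event is different from having it in the stated comparison, and that for renal and potassium data the general access provisions give no frequency and no by-arm table.

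A third reply concerns size. Section 18.3 links the formal looks to mortality, events of uncertain relationship escape the exempt list, and the attribution scale requires a documented alternative cause before an event is called not related. Filing could therefore be close to complete, and low filing fractions have no textual support. This is fair, and it is why the figures are an illustration only.

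A reader might also infer from section 23.5, which leaves other reportable events to university or local policy, that each site counts differently. Section 22.1 has all sites cede to one central IRB, so that inference is not supported.

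Finally, the attached charter and the stopping rules for the 50% analysis were not available for review. They may define the count.

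**Conclusion.** The point holds as a conflict in the text together with a gap in reporting. The stated harm criterion uses an undefined count, and the filing rules in 18.2 and 18.3 cannot all govern it. On the exemption reading, it relies on an attribution-filtered stream that the protocol itself calls inconsistent, for risks it ranks among the most severe. Renal and potassium events have no stated DSMB report.

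The size is unknown. Under the assumptions shown, the loss of power runs from small (0.41 to 0.35 at 90% filing) to large (0.41 to 0.14 at 50%). The conclusion rests on the wording and not on those figures. The documents do not show that attribution filtering will occur, that the comparison would be biased between arms, or that the DSMB is blind to these events. The point is worth fixing because it concerns the safety comparison and the remedy is cheap.

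**What to change.** - Reconcile the SAE collection, continuous-monitoring, laboratory, exemption and recording rules in 18.2 with 18.3 and the charter, so that one statement says which events the harm comparison counts. Define IRB-reported or drop it.
- State that the DSMB safety comparisons use by-arm rates, regardless of attribution, of outcomes already tracked: death, hypotension prompting intervention, escalation of respiratory support, new or worsening renal failure, and recorded potassium. The exemption from individual AE reporting can stay.
- Name renal and potassium data in the DSMB reports.
- Leave thresholds and the handling of several comparisons to the DSMB.
- Correct the reference to 5.1 and 5.2 so that it points to section 3.

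**Cost.** Wording in 18.2, 18.3 and possibly the charter, and a few rows in the DSMB tables. Section 1.6 already collects vasopressors, renal replacement therapy, creatinine, potassium and ventilatory support. Fluid boluses, needed for the hypotension endpoints in 3.3, are not listed there and may need one CRF field. The DSMB will have more comparisons to interpret. Potassium will be incomplete, because the table of events requires it only before enrollment and on days 1, 3 and 7, and otherwise records clinical values.

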## **19.0 Provisions to Protect the Privacy Interests of Participants**

*19.1 Protecting Privacy:* Conversations will be held in a private room whenever possible. Telephone calls will be performed one on one. The electronic consent process takes place using a secure RedCAP server that is HIPAA compliant.

*19.2 Access to Participants:* Conduct of the study and determination of both safety and efficacy of the intervention requires access of the medical records. All study personnel undergo human subjects protection training and understand and value privacy standards set forth by HIPAA. Participants enrolled in the trial are made aware during the informed consent procedure that study personnel will be required to access this private information for trial conduct, and consent to this access prior to agreeing to participate.

## **20.0 Compensation for Research-Related Injury**

*20.1 Compensation for Research-Related Injury:* There is no compensation available for research related injury from the study team. Due to the coronavirus public health crisis, the federal government has issued an order that may limit your ability to recover damages if you are injured or harmed while participating in this COVID-19 clinical study. If the order applies, it limits your ability to recover damages from the University, researchers, healthcare providers, study sponsor, manufacturer or

distributor involved with the study. However, the federal government has a program that may provide compensation to you or your family if you experience serious physical injuries or death due to this study. To find out more about this “Countermeasures Injury Compensation Program” go to <https://www.hrsa.gov/cicp/about/index.html> or call [name].

20.2 *Contract Language:* N/A.

## 21.0 Consent Process

21.1 *Consent Process (when consent will be obtained):* All subjects participating in this study or their LARs will be required to provide prospective informed consent using an eConsent platform. Prior to doing so, will discuss the study with study personnel who have been specially trained in obtaining informed consent. Our team has significant experience in this process, with due consideration of vulnerable patient populations. The subject or LAR will review the eConsent in detail and have the chance to ask questions. The personnel will then ask the subject questions to ensure that they understand the information presented in the consent discussion using a teach back method. The rights and welfare of the participants will be protected by emphasizing to them that the quality of their medical care will not be adversely affected if they decline to participate in this study. A copy of the informed consent document will be available electronically to the participants for their records. The participants may withdraw consent at any time throughout the course of the trial (see withdrawal procedures). The eConsent forms are included in this IRB submission.

21.2 *Waiver or Alteration of Consent Process (when consent will not be obtained):* N/A

21.3 *Waiver of Written/Signed Documentation of Consent (when written/signed consent will not be obtained):* N/A

21.4 *Non-English Speaking Participants:* Spanish and Somali speaking persons, who represent the vast majority of non-English speaking patients in the study hospitals and clinics, will be included as described above.

21.5 *Participants Who Are Not Yet Adults (infants, children, teenagers under 18 years of age):* Patients will be excluded per the study protocol. If logistical and scientific concerns can be adequately addressed, we will submit a revised application with an ethical framework, scientific support, and logistical considerations.

21.6 *Cognitively Impaired Adults, or adults with fluctuating or diminished capacity to consents:* To establish capacity in this setting, the MacArthur Competence Assessment tool will be administered by trained study personnel. If the patient lacks capacity, a LAR may provide consent for these participants on their behalf. For adults unable to consent, consent will be obtained from a legally authorized representative in the following order of priority consistent with Minnesota State Law: health care agent previously assigned via a health care power of attorney, spouse, parents, adult children, and then adult siblings. An incapacitated adult who has a court appointed guardian would require permission of the court for enrollment, and these participants will be excluded practically from the trial.

21.7 *Adults Unable to Consent:* The same process will be applied as in 21.6.

21.8 *Assent and dissent in adults with fluctuating or limited mental capacity:*

- **Assent:** If patients might have capacity, we use the MacArthur Competence Assessment Tool for Clinical Research. If they do not reach the pre-specified threshold for capacity, we seek from an LAR. We do not seek further assent, as these patients are frequently intubated, delirious, or medically sedated
- **Dissent:** However, even if the LAR consents to the trial, if the patient is awake and alert, but dissent, we will exclude the patient.

## 22.0 Setting

### 22.1 Research Sites:

- Participating study sites will undergo a standardized screening process to ensure they can participate in necessary aspects of the study protocol, and comply with safety and remote oversight, legal, and regulatory procedures. All sites will cede to the central (Advarra) IRB in addition to undergoing local context review, as appropriate.

### 22.2 International Research: N/A

## 23.0 Multi-Site Research

### 23.1 Study-Wide Number of Participants: 200 minimum, up to 220 including screen failures

### 23.2 Study-Wide Recruitment Methods: N/A

### 23.3 Study-Wide Recruitment Materials: N/A

### 23.4 Communication Among Sites:

#### 23.5 All sites have the most current version of the protocol, consent document(s), and, when applicable, HIPAA authorization.

- All required approvals (initial, continuing review, and modifications) have been obtained at each site (including by the site's IRB of record).
- All modifications have been communicated to sites, and approved (including approval by the site's IRB of record) before the modification is implemented.
- All engaged participating sites will safeguard data, including secure transmission of data, as required by local information security policies.
- All local site investigators conduct the study in accordance with applicable federal regulations and local laws.
- All non-compliance with the study protocol or applicable requirements will be reported in accordance with university or local policy.
- All other reportable events in accordance with university or local policy

### 23.6 Communication to Sites: Personnel from all sites will participate in monthly progress meeting calls, which will include discussion of any problems including reportable events, interim results, and completion of the study. More frequent communications may be planned, as becomes necessary.

## 24.0 Coordinating Center Research: N/A

